8.2. Secondary Efficacy Endpoint

The secondary endpoints for this study are the following:

- Day 28 all-cause mortality rate in the MITT population
- Day 14 and Day 28 all-cause mortality rate in the micro-MITT, extended micro-MITT, CE, ME, and CR-MITT populations
- The proportion of subjects with clinical success as evaluated by the investigator at Day 4, EOT, TOC, and LFU visits in the MITT, micro-MITT, extended micro-MITT, CE, ME, and CR-MITT populations
- The proportion of subjects with microbiological success at EOT, TOC, and LFU visits in the micro-MITT, extended micro-MITT, CR-MITT, and ME populations
- The proportional of subjects with microbiological success by pathogen at EOT, TOC, and LFU visits in the micro-MITT, extended micro-MITT, ME, and CR-MITT populations.
- The proportion of subjects with overall success at EOT, TOC, and LFU visits in the micro-MITT, extended micro-MITT, ME, and CR-MITT populations.

8.2.1. All-Cause Mortality Rate

The Day 14 and Day 28 all-cause mortality rate will be calculated as the percentage of subjects in each treatment group who experienced mortality, regardless of the cause, from randomization up to Day 14 or Day 28, the values recorded in the clinical database will be used for analyses.

8.2.1.1. All-Cause Mortality Rate Analysis

Day 14 and Day 28 all-cause mortality were analyzed in the different populations defined in Section 8.2 in a manner similar to the primary efficacy endpoints described in Section 8.1.2.1.

Provides a list of all-cause mortality rates for subjects at Day 14 and Day 28, in ascending order of subject number.

8.2.1.2. Subgroup Analysis of all-cause Mortality

All-cause mortality at Day 28 will be analyzed in the MITT population in subgroups similar to those described in Section 8.1.2.4.

8.2.1.3. By-pathogen All-cause Mortality Analysis

In the micro-MITT, extended micro-MITT, and CR-MITT populations, provide the proportion of subjects in each treatment group with all-cause mortality by pathogenic organisms at Day 14 and Day 28. For both treatment groups, subjects with unknown survival at Day 14 and Day 28 will not be considered dead.

In addition to the above analyses, in the micro-MITT, extended micro-MITT, and CR-MITT populations, the all-cause mortality rates at Day 14, and Day 28 will be presented for subjects in the corresponding dose groups by the species of Gram-negative pathogens detected in the subjects at baseline, for the MIC values of all detections at baseline IMI-XNW4107 and IMIREL.

8.2.2. Clinical Outcomes

The assessment of clinical outcome will be assessed by the investigator using the clinical outcome criteria as outlined below and carried out on Day 4, EOT, TOC, and LFU visit.

The clinical response criteria up to TOC visit will be defined as follows:

- **Success:**
 - For Day 4 visit: a subject is alive with resolution or improvement in at least 1 baseline sign/symptom AND no worsening of any baseline signs/symptoms AND no development of new signs/symptoms of pneumonia requiring the initiation of a non-study antibacterial therapy for the index infection.
 - For EOT or TOC visits: a subject is alive with complete resolution or significant improvement of signs and symptoms that were present at baseline and no new signs/symptoms of pneumonia, such that no further antibacterial therapy is necessary.
- **Failure:**
 - For Day 4 visit, persistence or worsening of baseline clinical signs and/or symptoms or the development of new clinical signs and/or symptoms of pneumonia requiring the initiation of a non-study antibiotic therapy or death of the subject.
 - For EOT and TOC visits, persistence, incomplete resolution or no significant improvement of baseline clinical signs and symptoms of pneumonia, and the need for further antibiotic therapy or death of the subject.
- **Indeterminate:** Study data are not available for evaluation of clinical response for any reasons other than due to the lack of clinical improvement or death.

The clinical response criteria at LFU visit will be defined as follows:

- **Sustained success:** Clinical success at TOC and continued resolution or substantial improvement of baseline signs and symptoms of pneumonia, such that no antibacterial therapy has been required for the treatment of pneumonia between TOC and LFU.
- **Failure:** Subject previously assigned a clinical failure or indeterminate at TOC; or relapse defined as clinical success at TOC, but recurrence of signs/symptoms of pneumonia, appearance of new signs and/or symptoms of pneumonia between TOC and LFU, and further antibiotic therapy is warranted or death of the subject.
- **Indeterminate:** Study data are not available for evaluation of clinical response for any reasons other than due to the lack of clinical improvement or death.
The clinical outcomes recorded in the clinical database will be used for analyses.

8.2.2.1. By-Subject Clinical Outcomes Analysis

The proportions of subjects with clinical success as evaluated by the investigator at Day 4, EOT, TOC, and LFU visits will be provided for each treatment group together with the treatment difference and the corresponding CIs for the MITT, micro-MITT, extended micro-MITT, CR-MITT, CE, and ME populations.

Treatment differences for clinical success will be analyzed in a similar way to the primary efficacy endpoint described in Section 8.1.2.1.

Death will be considered as a clinical failure. Subjects with missing or indeterminate clinical responses will be considered failures in the analyses in the MITT, micro-MITT, extended micro-MITT, CR-MITT and ME populations.

I In addition, the number and proportion of subjects having clinical outcome as success/sustained success, failure and indeterminate will be summarized by treatment group.

Provides a list of subjects' clinical outcomes, organized in ascending order by subject number.

8.2.2.2. By-Subject Clinical Outcomes Subgroup Analysis

Treatment for clinical success at D4, EOT, TOC, and LFU visits will be analyzed in the MITT population in subgroups similar to those described in Section 8.1.2.4.

8.2.2.3. By-Pathogen Clinical Outcomes Analysis

Proportion of subjects in the micro-MITT, extended micro-MITT, CR-MITT, and ME populations that provided clinical success by baseline pathogens at D4, EOT, TOC, and LFU exams for each treatment group.

In addition to the above analyses in the micro-MITT, extended micro-MITT, CR-MITT, and ME populations, the clinical cure rate at EOT, TOC, and LFU visits for subjects in the corresponding treatment groups will be listed by the species of gram-negative pathogens detected at baseline, and by the MIC values at baseline for IMI-XNW4107 and IMI\REL.

8.2.3. Microbiological Outcomes

Lower respiratory tract sample and blood culture data will be collected during the study and will be used in addition to the clinical response to programmatically assess the microbiological outcomes as defined below and carried out on EOT, TOC, and LFU visit.

- **Microbiological success** is based on the following rules:
 - **Eradication:** Absence of the baseline Gram-negative pathogen from an appropriate clinical specimen.
 - **Presumed eradication:** Absence of appropriate post-baseline culture material in a subject, but judged to be a clinical success.
- **Microbiological failure** is based on the following:
 - **Persistence:** Continued presence of the baseline Gram-negative pathogen from an appropriate clinical specimen. Persistence at EOT or TOC will be carried forward.
 - **Presumed persistence:** Absence of appropriate post-baseline culture material in a subject, but judged to be a clinical failure.
 - **Recurrence:** Recurrence of the baseline Gram-negative pathogen from an appropriate clinical specimen taken after TOC and the TOC culture shows eradication.
 - **Indeterminate:** No culture obtained from an appropriate clinical specimen and no clinical outcome is determined.

Pathogens first appearing after baseline in subjects with a different baseline pathogen are categorized as described below and will be considered separately from microbiological response.

- **Superinfection:** Isolation of new pathogen(s) (other than the original baseline pathogen[s]) from an appropriate clinical specimen during treatment with study drug that is accompanied by new or worsening signs and symptoms of infection requiring alternative antimicrobial therapy
 - Superinfection were assessed at the EOT visit with the rule that new pathogens other than the original baseline pathogen were isolated from appropriate lower respiratory tract clinical samples during the EOT visit or prior study drug therapy and were clinically assessed as failures.
- **New infection:** Isolation of new pathogen(s) (other than the original baseline pathogen[s]) from an appropriate clinical specimen after completion of study drug treatment that is accompanied by new or worsening signs and symptoms of infection requiring alternative antimicrobial therapy.

New infections are evaluated at the TOC and LFU visits with the rules:

- TOC visit: isolation of a new pathogen in addition to the original baseline pathogen from an appropriate lower respiratory tract clinical sample after the EOT visit, at or before the TOC visit, and a clinical assessment of failure;
- LFU visit: isolation of a new pathogen other than the original baseline pathogen from an appropriate lower respiratory tract clinical sample after the EOT visit, at or before the LFU visit, and a clinical assessment of failure.
- **Colonization:** Isolation of a new Gram-negative organism from a respiratory sample and no associated signs or symptoms of infection
Colonization was evaluated at EOT, TOC and LFU visits with the rules:
 - EOT visit: isolation of new gram-negative pathogens in addition to the original baseline gram-negative pathogens from appropriate lower respiratory tract samples at or prior to the EOT visit, but assessed clinically as successful
 - TOC visit: isolation of new gram-negative pathogens in addition to the original baseline gram-negative pathogens from appropriate lower respiratory tract samples after the EOT visit and at or before the TOC visit, but assessed clinically as successful.
 - LFU visit: isolation of new gram-negative pathogens in addition to the original baseline gram-negative pathogens from appropriate lower respiratory tract samples after the TOC visit and at or before the LFU visit, but clinically assessed as successful.

The microbiological data will be analyzed for descriptive statistics by subject and pathogen classification.

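### The SAP's rules for superinfection and new infection use clinical failure in place of new or worsening signs, so these descriptive rows partly track each arm's failures and deaths

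*SAP*

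**What the plan says.** SAP 8.2.3 gives each category a definition and then a rule by visit. It says that microbiological outcomes are derived by program from culture data and clinical response, so the visit rules are what would fill the tables.

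- **Definition of superinfection (on treatment) and new infection (after treatment).** A new pathogen "accompanied by new or worsening signs and symptoms of infection requiring alternative antimicrobial therapy".
- **Superinfection rule, EOT.** New pathogens "isolated from appropriate lower respiratory tract clinical samples during the EOT visit or prior study drug therapy and were clinically assessed as failures".
- **New-infection rules.** At TOC, a new pathogen after EOT, "at or before the TOC visit, and a clinical assessment of failure". At LFU, a new pathogen "after the EOT visit, at or before the LFU visit, and a clinical assessment of failure".
- **Clinical failure at EOT and TOC (SAP 8.2.2).** Signs that persist or resolve only in part count, alongside "no significant improvement of baseline clinical signs and symptoms of pneumonia, and the need for further antibiotic therapy or death of the subject". SAP 8.2.2.1 counts death as clinical failure and sets no limit on cause.
- **Clinical failure at LFU (SAP 8.2.2).** "Subject previously assigned a clinical failure or indeterminate at TOC", or relapse after success at TOC, or death.
- **Colonization (SAP 8.2.3).** Defined as "Isolation of a new Gram-negative organism from a respiratory sample and no associated signs or symptoms of infection". Its rules at EOT, TOC and LFU each require clinical success, and the LFU window starts after TOC.

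SAP 8.2.3 keeps these categories apart from microbiological response. SAP 8.2.3.3 reports their counts and proportions by treatment group.

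**The concern.** The definition asks whether the new organism came with something clinically new. The rule asks whether the subject failed. Failure at EOT or TOC can be met by the original pneumonia alone, or by a death unconnected with the lung, and nothing in the rule ties the failure to the new isolate. A failing or deceased subject also cannot be classed as colonized.

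A reader of the study report will take the row labels at their definitions. If one arm has more failures or deaths, it will tend to show more superinfection and new infection, and less colonization, even when the two arms acquire new organisms equally often.

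**Working it through.** There is no stated figure to reproduce. The check is a logical comparison of definition and rule, followed by a look at the windows and the direction of the error.

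**1. What the proxy tests.** Failure at EOT and TOC concerns baseline signs: "For EOT and TOC visits, persistence, incomplete resolution or no significant improvement of baseline clinical signs and symptoms of pneumonia". The Day 4 failure criterion in the same section does name worsening and newly developed signs, so the SAP draws this distinction elsewhere but not in the criterion that the rule uses.

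**2. Definition against rule, given a new isolate in the window.** Take four yes/no facts: new or worsening signs (N), unresolved baseline signs (B), need for further or alternative antibiotics (A), death (D). Treating the two antibiotic conditions as the same is generous to the rule.

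- Definition met = N and A.
- EOT/TOC rule met = D, or (B and A).

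Of the 2 × 2 × 2 × 2 = 16 combinations, 8 disagree:

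| N | B | A | D | Definition | Rule |
|---|---|---|---|---|---|
| no | yes | yes | no | no | yes |
| no | no | no | yes | no | yes |
| no | no | yes | yes | no | yes |
| no | yes | no | yes | no | yes |
| no | yes | yes | yes | no | yes |
| yes | no | no | yes | no | yes |
| yes | yes | no | yes | no | yes |
| yes | no | yes | no | yes | no |

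Seven are over-calls: one living subject with unresolved pneumonia and nothing new, and six deaths. One is an under-call: a living subject whose baseline signs have resolved but who has new signs needing treatment. These are counts of logical combinations, not expected frequencies.

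**3. The colonization side.** All three colonization rules require success, so none of the seven over-called combinations can reach that category, even when the isolate has no associated signs.

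**4. The LFU windows.** New infection at LFU counts isolates from after EOT; colonization at LFU counts isolates from after TOC. One isolate obtained between EOT and TOC can therefore be:

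- new infection at TOC and again at LFU, because a TOC failure is an LFU failure;
- colonization at TOC and new infection at LFU, if the subject succeeds at TOC and then relapses;
- in neither category at TOC but new infection at LFU, if the clinical outcome at TOC is indeterminate.

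**5. Direction, with assumed rates.** The documents give no isolation or failure rates by arm. Suppose that isolation of a new organism is equally frequent in both arms and independent of failure, and that the extra failures in one arm all come from the original pneumonia. Then rule-based superinfection = isolation rate × failure rate. With 15% isolation and failure of 25% against 35%:

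- 0.15 × 0.25 = 3.75%
- 0.15 × 0.35 = 5.25%

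The gap of 1.5 percentage points is entirely misclassification. For the same 10-point failure difference and isolation of 10% to 20%, the gap runs from 0.10 × 0.10 = 1.0 to 0.20 × 0.10 = 2.0 points. This shows how the rule behaves; it does not estimate this trial.

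**The case against.** The proxy is closer to the definition than it first looks. Success at EOT or TOC excludes new signs of pneumonia, so a subject with new signs cannot be a success; in practice an investigator would probably record the one under-called combination as a failure. A living failure at EOT or TOC must need further antibiotics, so much of the therapy element survives. LFU failure by relapse expressly covers new signs. All of this stands. What is lost is the requirement for something new or worse, the link to the isolate, and, for deaths, the therapy element as well.

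The death route is also narrow. It needs a new lower respiratory isolate within the window before death, and the SAP's revision table (section 14) describes mortality in the trial as low. That limits how often it occurs but does not make the rule right.

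Three stronger readings are tempting, and the documents do not support them:

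- **Every over-called subject is really colonized.** Colonization requires that no signs or symptoms be associated with the isolate. Persisting signs that cannot be attributed to one organism may fit neither definition.
- **Superinfection is overcounted several-fold.** Any such multiple is the reciprocal of an assumed share of isolates with new or worsening signs. If that share is taken as 25% to 50%, the result is 4- to 2-fold by construction.
- **The trial's efficacy conclusions are affected.** These categories do not enter microbiological success, overall outcome (SAP 8.2.4) or Day 14 mortality, and are not among the listed secondary endpoints (SAP 8.2).

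The text of protocol 7.5.8 on microbiological outcome is not in the public document, so whether the protocol contains the same rule cannot be checked.

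**Conclusion.** The point holds as a mismatch between definition and rule. Applied literally, the EOT, TOC and LFU rules count a new isolate as superinfection or new infection in subjects who do not meet the definition, and the colonization rules exclude every clinical failure and death. The unequal LFU windows add double counting and reclassification of the same isolate. No other SAP text corrects this.

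The consequence is limited to descriptive by-arm tables, whose rows will partly follow each arm's failure and death rates. The net error is likely to be overcounting of infection and undercounting of colonization, but its size cannot be estimated from the documents. The conclusion assumes that the visit rules are programmed as written and that clinical outcome is recorded by the SAP 8.2.2 criteria.

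**What to change.** Rewrite the visit rules in SAP 8.2.3 from the definitions:

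- **Superinfection or new infection:** a new pathogen, plus a sign or symptom that is new or worse around the isolate date (window fixed before unblinding), plus alternative antibacterial therapy started for it.
- **Colonization:** a new Gram-negative isolate with no associated signs or symptoms, whatever the clinical outcome.
- **New isolate, not classifiable:** all other new isolates, including death before any change of therapy and persisting signs that cannot be attributed. This row is needed because sending the remainder to colonization would contradict its definition and could mislabel a fatal new-pathogen pneumonia.
- **LFU:** count new infection only from isolates obtained after TOC.

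Add the extra row to the summary in SAP 8.2.3.3. Signs and symptoms are summarized at all visits (SAP 8.4.5), and medications are recorded with reasons and dates through LFU (protocol 6.1). The visible protocol text describes graded signs only at baseline and the schedule of assessments is redacted, so the sponsor should confirm that the post-baseline data are detailed enough.

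If they are not, keep the present logic, relabel the rows *new isolate with clinical failure* and *new isolate with clinical success*, and show deaths separately. If the SAP is already final, its section 1 provides for recording the change in the study report. The cost is SAP wording, a date-matching step and one more table row.

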8.2.3.1. Lower Respiratory Tract Sample Culture

Provide a list of the subject's lower respiratory tract sample cultures in ascending order of subject number.

8.2.3.2. Blood Culture

Provides a list of subject blood cultures, organized in ascending order by subject number.

8.2.3.3. By-Subject Microbiological Outcomes Analysis

Subject microbiological success was defined as all baseline infections with gram-negative pathogens were cleared.

The proportions of subjects with microbiological success at the EOT, TOC, and LFU visits will be provided for each treatment group together with the treatment difference and the corresponding CIs in the micro-MITT, extended micro-MITT, extended micro-MITT2, CR-MITT, and ME populations.

Treatment differences for microbiological success will be analyzed in a similar way to the primary efficacy endpoint described in Section 8.1.2.1.

Death will be considered as a microbiological failure. Subjects with missing or indeterminate microbiological responses will be considered failures in the analyses in the micro-MITT, extended micro-MITT, extended micro-MITT 2, and CR-MITT populations.

In addition, the number and proportion of subjects falling into each of the detailed microbiological outcome categories (Eradication, presumed eradication, persistence, presumed persistence, recurrence, indeterminate, superinfection, new infection and colonization) will be summarized by treatment group.

Provides a list of the microbiologic efficacy of the subjects, in ascending order of subject number.

8.2.3.4. By-Subject Microbiological Outcomes Subgroup Analysis

Treatment differences for microbiological success in the micro-MITT population at TOC visit will be analyzed in a similar way with the subgroup described in Section 8.1.2.4.

8.2.3.5. By-Pathogen Microbiological Outcomes Analysis

In the micro-MITT, extended micro-MITT, extended micro-MITT 2, CR-MITT, and ME populations, provide the proportion of subjects in each treatment group with microbiologic success and other microbiologic outcomes by pathogen on EOT, TOC, and LFU visits. Microbiological success will be summarized separately according to the subject's respective baseline Gram-negative pathogenic organisms. Other microbiological outcomes will be summarized according to the relative change of pathogenic bacteria after each baseline of the subjects.

In addition to the above analyses, in the micro-MITT, extended micro-MITT, CR-MITT, and ME populations, the microbiological success rate at EOT, TOC, and LFU visits for subjects in the corresponding treatment groups will be listed by the species of gram-negative pathogens detected at baseline, and by the MIC values at baseline for IMI-XNW4107 and IMI\REL.

8.2.4. Overall Outcomes

The overall outcome criteria are listed as the following:

- **Success:** Clinical success and microbiological success at the visits of EOT or TOC, or sustained success for clinical outcome and microbiological success at the visit of LFU. Microbiological success includes eradication or presumed eradication.
- **Failure:** Clinical failure and/or microbiological failure (persistence, presumed persistence or recurrence) at the visits of EOT, TOC and LFU.
- **Indeterminate:** Either clinical outcome or microbiological outcome, or both, are considered as indeterminate at the visits of EOT, TOC and LFU.

The clinical outcomes recorded in the clinical database and the microbiological outcomes from central laboratory will be used for analyses.

8.2.4.1. By-Subject Overall Outcomes Analysis

The proportions of subjects with overall success at EOT, TOC, and LFU visits will be provided for each treatment group together with the treatment difference and the corresponding CIs in the micro-MITT, extended micro-MITT, ME, and CR-MITT populations.

Treatment differences for overall success will be analyzed in a similar way to the primary efficacy endpoint described in Section 8.1.2.1.

Death will be considered as failure. Subjects with missing or indeterminate clinical or microbiological responses will be considered failures in the analyses in the micro-MITT, extended micro-MITT, and CR-MITT populations.

In addition, the number and proportion of subjects having overall outcome as success, failure and indeterminate will be summarized by treatment group.

Provides a comprehensive list of overall outcomes, organized in ascending order by subject number.

